9.4 Treatment

9.4.1 Treatment(s) Administered

Lenvatinib will be provided by Eisai as hard capsules containing 1, 4, or 10 mg lenvatinib. An extemporaneous suspension of lenvatinib capsules should be used for children unable to swallow capsules, as detailed in [Appendix 12](#).

Cohort 1 (Single-Agent Dose-Finding): Lenvatinib will be administered orally QD on Days 1 to 28 of each 28-day cycle ([Table 1](#)).

Cohort 2 (Single-Agent Expansion): Lenvatinib will be administered orally QD at the Single-Agent RD (identified in Cohort 1) on Days 1 to 28 of each 28-day cycle.

Cohort 3A (Combination Dose-Finding): Lenvatinib will be administered orally QD on Days 1 to 21 of each 21-day cycle ([Table 2](#))

Cohort 3B (Combination Expansion): Lenvatinib will be administered orally QD at the RD (identified in Cohort 3A) on Days 1 to 21 of each 21-day cycle. Ifosfamide and etoposide will be administered on Days 1 to 3 of each 21-day cycle.

Before dose administration on Day 1 of each cycle and prior to a change in dose due to dose reduction, the amount of lenvatinib needed for each subject must be calculated as follows:

$$\text{Scheduled dose (mg/m}^2\text{)} \times \text{body surface area (BSA) (m}^2\text{)} = \text{lenvatinib dose (mg)}$$

BSA will be calculated using the method that is accepted and customarily used by the clinical site. BSA must be calculated on Day 1 of each cycle based on the subject's current height and body weight. BSA will be used to determine the amount of lenvatinib for each subject. BSA should not be corrected for amputation. The dose should be rounded to the nearest whole number. After adjustment for BSA, the daily dose of lenvatinib should not exceed 24 mg daily.

9.4.1.1 Dose-Limiting Toxicity

Dose-limiting toxicity (DLT) in subjects treated with lenvatinib will be assessed according to CTCAE v4.03 ([Appendix 2](#)) and is defined as any of the following toxicities related to lenvatinib or chemotherapy drugs (ifosfamide and/or etoposide) occurring during Cycle 1 (Day 1 to Day 28) for Cohort 1, and Cycle 1 (Day 1 to Day 21) for Cohort 3A.

Hematologic Toxicity

- Grade 4 neutropenia for ≥ 7 days (≥ 10 days for Cohort 3A)
- Grade ≥ 3 thrombocytopenia with bleeding, or lasting >7 days (≥ 10 days for Cohort 3A)
- Grade ≥ 3 febrile neutropenia.(lasting ≥ 7 days for Cohort 3A)
- Next course of chemotherapy delayed for ≥ 7 days (Cohort 3A)

Non-Hematologic Toxicity

- Grade ≥ 3 nonhematological toxicity persisting more than 7 days despite optimal supportive care. Isolated laboratory abnormalities that resolve within a week, allergic reactions, and symptoms related to tumor progression will be excluded.
- Grade 4 hypertension, confirmed systolic or diastolic blood pressure more than 25 mmHg above the 95th percentile for age, or an elevated diastolic blood pressure (ie, >95 th percentile for age) not controlled by a single antihypertensive medication within 14 days of use. An antihypertensive tablet or capsule that contains up to two antihypertensive ingredient medications will count as one antihypertensive medication.
- Grade 3 proteinuria
- Any recurrent Grade 2 nonhematological toxicity requiring ≥ 2 interruption and dose reductions
- Any dose interruption or reduction due to toxicity which results in administration of less than 75% of the planned dosage of lenvatinib.
- Any other Grade ≥ 3 toxicity (hematologic and nonhematologic) assessed as related to lenvatinib treatment, and which in the opinion of the principal investigator and Eisai medical monitor constitutes a dose-limiting toxicity

All DLTs must be reported to the Eisai medical monitor within 24 hours of their occurrence. Determination of a DLT will be made by the investigator and the Eisai Medical Monitor, in consultation with the PSC, as needed. Subjects who discontinue the study treatment for any reason other than DLT during Cycle 1 (Day 1 through Day 28 for Cohort 1, and Day 1 through Day 21 for Cohort 3A) will be replaced.

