9.1.2 Treatment Phase

In all the cohorts, lenvatinib is administered daily (QD) and 1 treatment cycle is defined as a 28-day period for Cohorts 1, 2A, and 2B and a 21-day period for Cohorts 3A and 3B. A new treatment cycle begins every 28 days for Single-Agent Cohorts 1, 2A, and 2B or 21-day period for Combination-Treatment Cohorts 3A and 3B, irrespective of dose interruptions. See [Section 9.4.1](#) for rules regarding the calculation of lenvatinib dose based on body surface area (BSA).

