9.1.2.3 Cohort 3A: Combination Dose-Finding

Lenvatinib will be administered orally QD in combination with ifosfamide and etoposide from Day 1 to Day 3 of each cycle for a total of 5 cycles to subjects with relapsed or refractory osteosarcoma as described below and in Table 2. See [Section 9.4.3](#) for additional details on cytotoxic chemotherapy.

Table 2 Lenvatinib and Chemotherapy Doses for Combination Dose-Finding (Cohort 3A)

Dose Modification of Lenvatinib				
	Dose - Escalation	Starting Dose	De-escalation 1	De-escalation 2
Lenvatinib	RD (from Cohort 1)	20% lower than RD from Cohort 1	40% lower than RD from Cohort 1	60% lower than RD from Cohort 1

Dose Modification of Ifosfamide and Etoposide				
	No Dose Escalation	Starting Dose	De-escalation 1*	De-escalation 2*
Ifosfamide		3000 mg/m ² /day IV for 3 days	2400 mg/m ² /day IV for 3 days	1800 mg/m ² /day IV for 3 days
Etoposide		100 mg/m ² /day IV for 3 days	80 mg/m ² /day IV for 3 days	60 mg/m ² /day IV for 3 days

RD = recommended dose, *each De-escalation dose level is 20% lower than the Starting Dose.

The chemotherapy cycles will be repeated every 21 days.

Lenvatinib is administered daily as a QD dose, and ifosfamide and etoposide will be administered on Days 1 to 3 of each cycle for a total of 5 cycles. Each Chemotherapy cycle is repeated every 21 days. Six subjects with osteosarcoma (who have not received prior lenvatinib) will be enrolled first to Cohort 3A at the Starting Dose of lenvatinib (20% below the Single-Agent RD in Cohort 1) in combination with ifosfamide 3000 mg/m²/day for 3 days (ifosfamide total dose 9 g/m²) and etoposide 100 mg/m²/day for 3 days (etoposide total dose 300 mg/m²). Subjects with lenvatinib dose capped after BSA adjustment (dose must not exceed 24 mg daily) actually take lower dose level than assigned. If a subject with capped dose experiences a DLT, the DLT data from that subject will be counted to determine the RD of the combination treatment. A subject with capped dose who does not experience a DLT will be replaced for the purpose of determining the RD.

DLTs occurring during Cycle 1 will be evaluated and the next 6 subjects will be assigned a dose based on the rules for Dose Escalation and Dose De-Escalation as follows:

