- a. If ≤ 1 out of 6 subjects experiences a DLT at the starting dose during Cycle 1 (Day 1 to Day 21), then assign 6 more subjects to the next higher dose level of lenvatinib (RD from Cohort 1) and keep the chemotherapy dose the same (starting dose).
- b. If ≥ 2 out of 6 subjects experience a DLT at the starting dose during Cycle 1 (Day 1 to Day 21), then follow the instructions below:
 - i. If ≥ 2 subjects experience hematologic DLT and ≤ 1 subject experiences non-hematologic DLT, then assign 6 more subjects to 20% lower doses (De-escalation 1) of ifosfamide and etoposide and keep the lenvatinib dose the same; or
 - ii. If ≥ 2 subjects experience non-hematologic DLT and ≤ 1 subject experiences a hematologic DLT, then assign 6 more subjects to a 20% lower dose of lenvatinib (De-escalation 1) and keep the ifosfamide and etoposide doses the same; or
 - iii. If ≥ 2 subjects experience hematologic DLTs and ≥ 2 subjects experiences non-hematologic DLTs, then assign 6 more subjects to 20% lower doses of lenvatinib, ifosfamide, and etoposide each (De-escalation 1); or
 - iv. If only 1 subject experiences a hematologic DLT and only 1 subject experiences a non-hematologic DLT, then assign 6 more subjects to the same dose level of lenvatinib, ifosfamide and etoposide each.

c. Continue the above processes until the combination dose of lenvatinib, ifosfamide and etoposide results in ≤ 1 DLT per 6 subjects or only 1 subject experiences a hematologic DLT and only 1 subject experiences a nonhematologic DLT per 6 subjects upon repeating the same dose level. This dose will be considered as the RD of the combination treatment.

Once the RD has been determined, subjects treated at a lower dose level should continue to be treated at that dose level. Intrasubject dose-escalation is not permitted. Further dose de-escalation of lenvatinib or the chemotherapy dose may be considered (pending discussion with the Protocol Steering Committee [PSC]), if needed.

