9.4.3 Cytotoxic Chemotherapy: Ifosfamide and Etoposide

The cytotoxic chemotherapy drugs (used in combination with lenvatinib) in this study will be ifosfamide and etoposide. These chemotherapy drugs will be provided by the sponsor. The administration procedure should follow the approved prescribing information in each country/region. The chemotherapy regimen schedule and dosing details are provided below.

The chemotherapy regimen schedule will consist of ifosfamide 3000 mg/m²/day IV infusion over 30 minutes for 3 consecutive days (Day 1 to Day 3 of each cycle) and etoposide 100 mg/m²/day IV infusion for 3 consecutive days (Day 1 to Day 3 of each cycle). Chemotherapy administration should be accompanied by vigorous hydration and administration of mesna according to the institutional guidelines. Each chemotherapy cycle will be 21 days for a total of 5 cycles.

Pegylated G-CSF or G-CSF will be administered at least 24 to 72 hours after completion of ifosfamide-etoposide chemotherapy until WBC counts are $\geq 1 \times 10^9/L$ or at the investigator's discretion.

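### Cohort 3A's Day 1–21 DLT window closes before one listed DLT, a delay of at least 7 days in chemotherapy course 2, can be established (about Day 29)

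*Protocol*

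**What the plan says.** Protocol 9.4.1.1 limits DLTs to listed toxicities arising in Cycle 1, "and Cycle 1 (Day 1 to Day 21) for Cohort 3A". Under hematologic toxicity, for Cohort 3A only, it lists "Next course of chemotherapy delayed for" at least 7 days. The synopsis and SAP 13.1 carry the same window and the same criterion.

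Protocol 9.4.3 fixes the interval: "Each chemotherapy cycle will be 21 days for a total of 5 cycles". Protocol 9.1.2 starts a new cycle after each "21-day period for Combination-Treatment Cohorts 3A and 3B, irrespective of dose interruptions".

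Protocol 9.1.2.3 (repeated in SAP 3.3.4.3) drives dose assignment from this count: "DLTs occurring during Cycle 1 will be evaluated and the next 6 subjects will be assigned a dose". Rules a and b restate the Day 1 to Day 21 window. Two or more hematologic DLTs with at most one nonhematologic lead to rule b.i: "then assign 6 more subjects to 20% lower doses (De-escalation 1) of ifosfamide and etoposide". Rule b.iv covers the one-plus-one result: "only 1 subject experiences a hematologic DLT and only 1 subject experiences a non-hematologic DLT, then assign 6 more subjects to the same dose". Rule c accepts a dose on at most one DLT in six, or on one plus one "per 6 subjects upon repeating the same dose level".

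SAP 5.6.1.4 says Cohort 3A DLTs were recorded on Day 1 to Day 21. In SAP 5.2.1 the second route into the Cohort 3A DLT Analysis Set is for subjects who took every scheduled Cycle 1 dose and finished Cycle 1 observation DLT-free.

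**The concern.** The window and the criterion do not fit together. A delay of the next course can only begin once that course is due, and it is due after the window has closed. On the literal text, a subject whose only qualifying event is a late course 2 is DLT-free both for rules a to c and for the DLT Analysis Set, although the protocol lists that event as dose-limiting. On the reading the authors evidently had in mind, the subject has a DLT. The same data can therefore give two DLT counts, and the dose rules act on the count.

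Timing is a separate matter. Even if the delay counts, the protocol assigns the next six subjects on Cycle 1 DLTs and states no further wait, so a dose step can be taken before the criterion can be assessed in the most recently treated subjects.

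**Working it through.** The plan states no error rate or other operating characteristic for Cohort 3A, only 12 to 24 subjects (two to four sets of six), so there is no figure of its own to reproduce.

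**Timing.** Inputs: window ends Day 21 (Protocol 9.4.1.1; SAP 13.1 and 5.6.1.4); course interval 21 days (Protocol 9.1.2.3 and 9.4.3); delay threshold 7 days (Protocol 9.4.1.1); tolerance ±1 day (Protocol Table 9, footnote a; SAP 8.1).

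- Course 2 due: 1 + 21 = Day 22.
- Earliest day a 7-day delay is established: 22 + 7 = Day 29.
- Gap to the end of the window: 29 − 21 = 8 days.
- With the tolerance, course 2 is due Day 21 to 23, the delay is established Day 28 to 30, and the gap is 7 to 9 days.
- If the next set is assigned on the sixth subject's Day 22, the decision comes 29 − 22 = 7 days too early for that subject.

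For the delay to be complete by Day 21, course 2 would have to be due by Day 14 (14 + 7 = 21). Nor can a delay stretch Cycle 1, because Protocol 9.1.2 fixes the 21-day cycle.

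**Comparison with other duration criteria.** An event needing L days fits if its onset is no later than Day 21 − L + 1. Grade 4 neutropenia or Grade ≥3 thrombocytopenia for 10 days: onset by Day 12. Febrile neutropenia for 7 days: by Day 15. Nonhematologic toxicity for more than 7 days (8 days): by Day 14. Each can be met inside the window; the delay criterion cannot.

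**Effect on the rules.** Let h and n be the counted hematologic and nonhematologic DLTs among six subjects, one type per subject, and add one delay to h, where the protocol lists it.

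| Counted (h, n) | Rule without the delay | Rule with it |
|---|---|---|
| (0, 0) | a | a; a second delay gives b.i |
| (1, 0) | a: raise lenvatinib | b.i: lower chemotherapy |
| (0, 1) | a | b.iv: repeat the level |
| (1, 1) | b.iv, or acceptance under rule c on a repeat | b.i |
| (1, 2 or more) | b.ii: lower lenvatinib | b.iii: lower all three drugs |

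On a repeated level, (0, 1) does not change, because rule c accepts both (0, 1) and (1, 1). There (1, 0) moves from acceptance to b.i. So a single delay changes the step whenever exactly one hematologic DLT is already counted, and at a first-time level also when the only counted DLT is nonhematologic.

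**The case against.** The best answer is that nobody would read the criterion out of existence. It was written for Cohort 3A alone, the next course after Cycle 1 can only be course 2, and the window governs when the toxicity occurs, not when a qualifying period ends. Other criteria also need an onset-based reading at times: neutropenia beginning after Day 12, or diastolic pressure whose 14 days of treatment begin after Day 8, cannot be completed by Day 21. SAP 5.6.1.4 takes its DLT reasons from SAP 13.1, which includes the delay, so it appears to treat the delay as recordable; the subject would then enter the DLT Analysis Set by its first route, as having had a DLT. This stands as the likely intent. But no sentence says so, and it leaves the timing gap untouched.

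Oversight also counts. The investigator and medical monitor determine DLTs, with the Protocol Steering Committee (PSC) as needed. The sponsor evaluates risk and benefit throughout, further de-escalation can be discussed, and SAP 6 provides a PSC review after treatment in Cohort 3A is complete. By then course 2 dates would probably be known. This mitigates the risk, but it neither defines what counts nor makes an intermediate step wait.

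Three stronger inferences are tempting and not supported:

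- *That delay-only cases are common.* A reader might point to the one-week chemotherapy hold in Protocol Table 4 for creatinine 1.5–3 × ULN, a range that SAP 13.3 grades as 2. Chemotherapy is given only on Days 1 to 3, so a hold starting between Day 4 and Day 15 has expired by Day 22 (15 + 7 = 22) and delays nothing. Only a rise near Day 22, or a prolonged hold, would matter, and a renal cause fits poorly under a hematologic heading.
- *That a given share of dose steps would differ.* The rows of the table are not equally likely. The documents give no DLT or delay rates, so any percentage would come from assumed inputs.
- *That the recommended dose is wrong.* SAP 3.4.2 sets it at the top level of Table 2, lenvatinib 14 mg/m² with unreduced chemotherapy. If the rules were followed, the levels passed on at most one DLT in six, or one plus one on a repeat. An uncounted delay could alter such results, but nothing shows that one occurred.

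**Conclusion.** The inconsistency is real and lies in the text: a listed Cohort 3A safety criterion cannot be met before about Day 29 (Day 28 to 30 with the tolerance), while counting stops at Day 21. Literally, it never counts. As intended, it counts but may not be known when six more subjects are assigned. One delay is enough to change the next step in the situations tabulated, assuming one DLT type per subject and that the delay is classed as hematologic.

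No frequency can be attached, and neither a missed DLT nor a wrong recommended dose is shown. Because the dose is already set, what is at stake now is whether the Cohort 3A DLT count can be reproduced under one stated rule, and whether the rule is sound if reused.

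**What to change.** In SAP 13.1, 5.6.1.4 and the Cohort 3A DLT Analysis Set in 5.2.1, add one sentence: a delay of course 2 by 7 days or more, due to treatment-related toxicity arising in Cycle 1, counts as a Cycle 1 DLT and is assessed until course 2 starts or Day 29 (Day 30 with the tolerance), whichever comes first.

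Check course 2 dates for the Cohort 3A subjects, and report in the CSR whether any decision under rules a to c, including the one-plus-one acceptance route, would change. The cost is three short edits and a check of about 12 to 24 subjects (SAP 4) from dose records that SAP 5.6.1.3 already lists. No new data are needed.

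If Protocol 9.4.1.1 is amended or reused, add the same sentence and hold each 6-subject decision until the criterion can be assessed. The price is up to about 8 days per dose step (29 − 21), or one more if the tolerance is used.

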9.4.1.2 Lenvatinib Dose Reduction and Interruption Instructions

Dose adjustments will be made for subjects who experience treatment-related toxicity according to the instructions provided in the [Table 3](#). Doses in the Dose Adjustment column are based on a presumed starting dose of 11 mg/m².

Dose reductions occur in succession based on the previous dose level. Each dose level reduction is a 20% reduction from the previous dose. Once the dose has been reduced, it cannot be increased at a later date.

Table 3 Criteria for Temporary Discontinuation of Study Drug, Dose Reduction, and Resumption of Treatment

Lenvatinib Related Toxicity ^{a, b} including hepatic injury and thromboembolic events	Management	Dose Adjustment
Grade 1		
	Continue treatment	No change
Intolerable Grade 2^c or Grade 3^e		
First occurrence	Interrupt until resolved to Grade 0 - 1 or baseline	8.8 mg/m ² (or 20% reduction of the starting dose) orally QD (one-level reduction)
Second occurrence		
(same toxicity or new toxicity)	Interrupt until resolved to Grade 0 - 1 or baseline	7.0 mg/m ² (or 20% reduction of the previous dose) orally QD (one-level reduction)
Third occurrence		
(same toxicity or new toxicity)	Interrupt until resolved to Grade 0 - 1 or baseline	5.6 mg/m ² (or 20% reduction of the previous dose) orally QD (one-level reduction)
Fourth occurrence		
(same toxicity or new toxicity)	Interrupt until resolved to Grade 0 - 1 or baseline	Discuss with sponsor
Grade 4^d: Discontinue Study Treatment		

For grading, see Common Terminology Criteria for Adverse Events (CTCAE v4.03) ([Appendix 2](#)). Collect all CTC grades of adverse events, decreasing and increasing grade.

- a. Interruption of lenvatinib treatment for more than 28 days (due to lenvatinib-related toxicities) will require a discussion with the sponsor before treatment can be resumed.
- b. Initiate optimal medical management for nausea, vomiting, and/or diarrhea before any lenvatinib interruption or dose reduction.
- c. Applicable only to those Grade 2 toxicities judged by the subject and physician to be intolerable. Not applicable to abnormal clinical laboratory values that are not clinically relevant based on the judgment of the investigator.
- d. Excluding laboratory abnormalities judged to be non-life-threatening, in which case manage as Grade 3.
- e. Obese subjects with weight loss do not need to return to baseline or Grade 1 weight loss to restart lenvatinib. There should be no weight loss for at least 1 week, and subjects should be started at the lower dose and normal BMI should be used for future dose reductions. Obesity is defined as body mass index (BMI) percentiles corresponding to 30 kg/m², related to the age of the children. ([Cole T.J., et al 2000](#)) or BMI \geq the 95th percentile for children and teens of the same age and sex ([Ogden CL et al, 2002](#)) ([Appendix 9](#) and [10](#)).

9.4.1.3 Blood Pressure

For children, blood pressure varies by the sex and age of the child and it is closely related to height and weight. Blood pressure will be assessed in terms of percentile for sex, age and height/length. Guidelines to sex, age, and height-specific percentiles of blood pressure is provided in [Appendix 7](#) and [Appendix 8](#). Blood pressure that is consistently above the 95th percentile [for subjects age 18-25 years BP \leq 140/90 mm Hg] for age and height/length requires further evaluation. A referral to a cardiologist is recommended for patients who develop hypertension during the study. Ideally, cardiovascular assessments and the management of hypertension should be supervised by a cardiologist. Exercise, excitement, coughing, crying and struggling may raise the systolic pressure of children as much as 40 to 50 mmHg greater than their usual level. Variability in blood pressure in children of approximately the same age and body build should be expected and serial measurements should always be obtained when evaluating a patient with hypertension. **BP values for management of hypertension for subjects 18 to 25 years of age are included in parenthesis.**

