- b: Initiate optimal medical management for nausea, vomiting, and/or diarrhea prior to any study treatment, interruption, or dose reduction.
- c: Applicable only to Grade 2 toxicities judged by the subject and/or physician to be intolerable. Not applicable to abnormal clinical laboratory values that are not clinically relevant based on the judgment of the investigator.
- d: Excluding laboratory abnormalities judged to be non-life-threatening, in which case manage as Grade 3.
- e: Obese subjects with weight loss do not need to return to baseline or Grade 1 weight loss to restart lenvatinib. There should be no weight loss for at least 1 week, and subjects should be started at the lower dose and normal Body Mass Index (BMI) should be used for future dose reductions. Obesity is defined as body mass index (BMI) percentiles corresponding to 30 kg/m², related to the age of the children. ([Cole TJ., et al 2000](#)) or BMI \geq the 95th percentile for children and teens of the same age and sex. ([Ogden CL et al, 2002](#)) ([Appendix 9](#) and [10](#)).

Blood Pressure

For children, blood pressure varies by sex and age of the child and is closely related to height and weight. Blood pressure will be assessed in terms of percentile for sex, age, and height/length. Guidelines to sex, age, and height-specific percentiles of blood pressure are provided in [Appendix 7](#) and [Appendix 8](#). Blood pressure that is consistently above the 95th [for subjects age 18-25 years BP $>150/90$ mm Hg] percentile for age and height/length requires further evaluation. A referral to a cardiologist is recommended for patients who develop hypertension during the study. Ideally, cardiovascular assessments and the management of hypertension should be supervised by a cardiologist. Exercise, excitement, coughing, crying, and struggling may raise the systolic pressure of children as much as 40 to 50 mmHg greater than their usual level. Variability in blood pressure in children of approximately the same age and body build should be expected and serial measurements should always be obtained when evaluating a patient with hypertension. **BP values for management of hypertension for subjects 18 to 25 years of age are included in parenthesis.**

Management of Hypertension

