≥ 16 years	1.7	1.4

The threshold creatinine values in this Table were derived from the Schwartz formula for estimating GFR ([Schwartz, et al., 1985](#)) using child length and stature data published by the CDC.

- b. Urine dipstick $< 2+$ for proteinuria. Subjects who have $\geq 2+$ proteinuria on dipstick urinalysis should undergo a spot protein-creatinine (P/C) ratio test that should be Grade < 2 per CTCAE v4.03 and if possible perform a 24-hour urine collection (children and adolescents ≤ 12 years of age must have $\leq 500 \text{ mg}$ of protein/24 hours and subjects > 12 years of age must have $\leq 1 \text{ g}$ of protein/24 hours)
- c. No clinical evidence of nephrotic syndrome

13. Adequate cardiac function as evidenced by left ventricular ejection fraction $\geq 50\%$ at baseline as determined by echocardiography

14. Adequately controlled blood pressure (BP) with or without antihypertensive medications, defined as:

BP <95th percentile for sex, age, and height/length at screening (as per National Heart Lung and Blood Institute guidelines; see [Appendix 7](#) and [Appendix 8](#)) and no change in antihypertensive medications within 1 week prior to Cycle 1/Day 1. Osteosarcoma subjects age 18 to 25 years should have BP \leq 150/90 mm Hg at screening and no change in antihypertensive therapy within 1 week prior to Cycle 1 Day 1.

15. Washout of 3 weeks in case of prior chemotherapy, 6 weeks if treatment included nitrosoureas; 4 weeks for definitive radiotherapy, and 2 weeks for palliative radiotherapy; 3 months from high-dose chemotherapy and stem cell rescue; 3 weeks from major surgery. Subjects must have recovered from the acute toxic effects of all prior anticancer therapy before enrollment into the study
16. Written and signed informed consent from the parent(s) or legal guardian and assent from the minor subject. Written informed consent from subjects \geq 18 years.
17. Willing and able to comply with the protocol, scheduled follow-up, and management of toxicity as judged by the Investigator

Cohort 3B (Combination Expansion): Osteosarcoma subjects who progressed in Cohorts 1 or 2B and opt to receive combination therapy:

18. Osteosarcoma subjects receiving combination therapy of lenvatinib with ifosfamide and etoposide should meet only Inclusion Criteria Numbers 7 6 through 17 (after progression in Cohort 2B)

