9.4.1.4 Management of Hypertension

Hypertension is a recognized side-effect of treatment with drugs inhibiting vascular endothelial growth factor (VEGF) signaling. Investigators should therefore ensure that subjects enrolled to receive treatment with lenvatinib have BP $<$ 95th percentile [BP \leq 150/90 mm Hg] for sex, age, and height/length at the time of study entry and, if known to be hypertensive, have been on a stable dose of antihypertensive therapy for at least 1 week before Cycle 1 Day 1. Early detection and effective management of hypertension are important to minimize the need for lenvatinib dose interruptions and reductions. Antihypertensive agents should be started as soon as elevated BP (systolic BP \geq 95th percentile [BP \geq 140 mm Hg] or diastolic BP \geq 95th percentile [BP \geq 90 mm Hg]) is confirmed on 2 assessments obtained 1 hour apart. One BP assessment is defined as the mean value of 3 measurements obtained at least 5 minutes apart. The choice of antihypertensive treatment should be individualized to the subject's clinical circumstances and follow standard medical practice. For previously normotensive subjects, monotherapy with one of the classes of antihypertensives should be started when systolic BP \geq 95th percentile [BP \geq 140 mm Hg] or diastolic BP \geq 95th percentile [BP \geq 90 mm Hg] is first observed on 2 assessments obtained 1 hour apart. For those subjects already on antihypertensive medication, the dose of the current agent may be increased, if appropriate, or 1 or more agents of a different class of antihypertensive should be added. For subjects with hypertension and proteinuria, treatment with an angiotensin-converting enzyme (ACE) inhibitor or angiotensin-II receptor antagonist is preferred.

Lenvatinib should be withheld in any instances where a subject is at imminent risk to develop a hypertensive crisis or has significant risk factors for severe complications of uncontrolled hypertension (eg, BP \geq 99th percentile [BP \geq 160/100 mm Hg], significant risk factors for cardiac disease, intracerebral hemorrhage, or other significant comorbidities). Once the subject has been on the same antihypertensive medications for at least 48 hours and the BP is controlled, lenvatinib should be resumed as described below.

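### For subjects aged 18 to 25, the blood pressure requiring further evaluation is >150/90 mm Hg in the synopsis but <=140/90 mm Hg in Section 9.4.1.3, and the adult values standing for the 95th percentile conflict elsewhere

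*Protocol*

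**What the plan says.** The sentence on further evaluation appears twice in the current protocol text, with the same action attached and an adult bracket that opens "for subjects age 18-25 years BP" in both places.

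- Synopsis, Blood Pressure: the adult bracket is "for subjects age 18-25 years BP $>150/90$ mm Hg".
- Section 9.4.1.3: the sentence opens "Blood pressure that is consistently above the 95th percentile", the adult bracket is "for subjects age 18-25 years BP \leq 140/90 mm Hg", and it closes "for age and height/length requires further evaluation".

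Section 9.4.1.3 adds that the bracketed figures are the values for managing hypertension at ages 18 to 25.

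Three other rules give an adult value in place of the 95th percentile:

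- **Starting treatment** (synopsis and Section 9.4.1.4): "Antihypertensive agents should be started as soon as elevated BP" is confirmed on two assessments, with at or above the 95th percentile bracketed as systolic >=140 or diastolic >=90.
- **Ending two-weekly monitoring, and restarting lenvatinib after an interruption** (synopsis and Section 9.4.1.4): below the 95th percentile is bracketed as systolic <=150 and diastolic <=95.
- **Entry** (inclusion criterion 14 and the opening of Section 9.4.1.4): below the 95th percentile is bracketed as "BP \leq 150/90 mm Hg] for sex, age, and height/length at the time of study entry".

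The percentile tables in Appendices 7 and 8 stop at age 17. Footnote i of Tables 8 and 9, which cover Cohorts 2B, 3A and 3B, sends sites to Section 9.4.1.3 and Figure 2.

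**The concern.** For ages 18 to 25 the brackets are the only numerical criterion, because the appendix tables offer no percentile to fall back on. One bracket has two values, and the visit-schedule footnotes send sites to the version with the reversed sign. A site working from the synopsis and one working from Section 9.4.1.3 can reach different decisions on whether the same reading needs evaluation.

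The second strand concerns the cut-point itself. In the percentile wording, below the 95th and at or above the 95th are complementary. Their adult translations are not, so one reading can fall on both sides.

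This bears on safety conduct. The protocol describes hypertension as a recognized effect of this drug class and says that early detection and effective management limit dose interruptions and reductions.

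**Working it through.** No formula applies, so the check sets the rules side by side and runs example readings through them. A slash value is taken to be exceeded when either component is exceeded, in line with the treatment-start rule.

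**1. The further-evaluation sentence**

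| Reading (mm Hg) | Synopsis, >150/90 | 9.4.1.3 as printed, <=140/90 | 9.4.1.3 with the sign turned, >140/90 |
|---|---|---|---|
| 120/80 | not flagged | flagged | not flagged |
| 145/85 | not flagged | not flagged | flagged |
| 155/95 | flagged | not flagged | flagged |

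The third column cannot be intended, since the sentence itself speaks of pressure above the percentile. The fourth column shows that turning the sign alone does not settle the matter. The diastolic figure is 90 in both versions, so the remaining difference is systolic above 140 but not above 150 with diastolic not above 90. In whole numbers that is systolic 141 to 150 with diastolic <=90.

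**2. The adult equivalents of the 95th percentile**

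| Rule | Percentile wording | Adult bracket | 145/92 | 145/85 |
|---|---|---|---|---|
| Start antihypertensives | >=95th | >=140 or >=90 | met | met |
| Restart lenvatinib, end extra monitoring (blood-pressure part) | <95th | <=150 and <=95 | met | met |
| Entry | <95th | <=150/90 | not met (92 > 90) | met |

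The exact complement of the first row is systolic <140 and diastolic <90. The second row instead uses 150 and 95. The overlap is therefore every reading with systolic <=150 and diastolic <=95 that also has systolic >=140 or diastolic >=90. For 145/92, 145 >= 140 and 92 >= 90 put it at or above the cut-point, while 145 <= 150 and 92 <= 95 put it below. The entry bracket agrees with neither row: it shares systolic 150 with the second and the figure 90 for diastolic with the first.

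**3. What is consistent**

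The treatment-start rule (>=140 or >=90) and the upper rule (>=160 or >=100) read the same in the synopsis and in Section 9.4.1.4.

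**The case against.** The strongest reply is that little turns on the disputed sentence. The treatment-start rule is identical in both places and already covers systolic 141 to 150, so a confirmed 145/85 calls for treatment whichever version of the evaluation sentence is read. This stands. A reader might infer that the 18-to-25 group has no usable trigger at all; the documents do not support that.

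A reader might also infer that the body text directs sites to investigate normal pressure. Taken literally the bracket does so, but the words of the sentence state the opposite direction, so the sign is evidently a drafting error. A conversion error in the extracted text cannot be excluded either. The 150 versus 140 difference remains in both cases.

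Another tempting inference is that sites will record hypertension at different levels and so distort the safety results. This is not shown. Blood pressure is measured at scheduled visits, adverse events are graded by CTCAE v4.03, SAP Section 5.6.2 summarizes hypertension by CTCAE grade, and the percentile shift table in SAP Section 5.6.4 covers only subjects under 18. Nor does the hypertension DLT criterion in Section 9.4.1.1 cite these brackets.

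Finally, an entry ceiling may differ from a treatment-start level: a subject at 145/85 can be enrolled and then treated, and both instructions are followed. On that ground "Osteosarcoma subjects age 18 to 25 years should have BP" at or below 150/90 is not in itself a contradiction. Restart values could likewise be set apart from start values on purpose. But the text presents each bracket as the adult counterpart of the same percentile and gives no sign that different levels were meant.

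**Conclusion.** The inconsistency holds, within limits. The adult evaluation trigger differs between the synopsis and Section 9.4.1.3 in both value and sign. Read in the direction of the sentence's own words, the disagreement covers systolic 141 to 150 mm Hg with diastolic <=90, and only the evaluation step. Separately, the 95th percentile has two systolic equivalents (140 and 150) and two diastolic equivalents (90 and 95) across the start, restart, monitoring and entry rules.

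The point affects subjects aged 18 to 25, whom SAP Section 5.2.4 places in Cohorts 2B, 3A and 3B. It does not touch sample size, power or type I error. It is an error in a safety threshold in operative text, and it should be corrected even though a consistent treatment trigger exists.

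The 141-to-150 band assumes that either component alone is enough to exceed a slash value. Figure 2 was not available in the copy reviewed, so its adult values could not be compared. No view is taken on which threshold is right.

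**What to change.** Issue a protocol clarification that:

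1. gives one adult bracket for the further-evaluation sentence in the synopsis and Section 9.4.1.3, with a sign that agrees with the words of the sentence;
2. reconciles the adult values for the 95th percentile across the treatment-start, monitoring and restart rules (synopsis and Section 9.4.1.4) and the entry limit (inclusion criterion 14 and Section 9.4.1.4);
3. says so explicitly wherever different levels for different actions are intended, and does not then present them as equivalents of one percentile;
4. checks Figure 2 against the result.

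The clinical team should choose the values. The cost is the clarification and its notification to sites; no statistical analysis changes.
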